6.3.4 Rapid progression

As recent preclinical data has shown that PD-1 may act as a tumor suppressor in T-cell malignancies(21), and three patients with ATLL who received the anti-PD-1 antibody Nivolumab experienced progression of disease shortly after receiving the first dose (NCT02631746, unpublished data), rapid progression will be followed as a distinct outcome. Rapid progression is defined as any PD within 14 days of the first avelumab administration (i.e., up to and including Cycle 1, Day 21), excluding skin flares. Patients who are suspected of having a skin flare during this period but have confirmed PD on re-evaluation will be noted to have had rapid progression.

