3.8.1 Criteria for removal from protocol therapy

Patients who meet the following criteria should be discontinued from protocol therapy:

- Completion of protocol therapy (i.e., up to 6 cycles)
- Confirmed disease progression
- Intercurrent illness that prevents further administration of treatment
- Unacceptable toxicities as listed in Section [3.1.1](#) or those toxicities listed in Section [3.3](#) that require treatment to be stopped
- More than 6 weeks has elapsed since the patient received protocol therapy
- Subject's request to withdraw from protocol therapy
- Investigator's decision to withdraw the patient
- Subject's non-compliance with trial treatment or procedure requirements that requires removal in the opinion of the PI
- Pregnancy
- The drug manufacturer can no longer prove the study agent
- Study is cancelled for any reason

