10 STATISTICAL CONSIDERATIONS

10.1 STATISTICAL HYPOTHESIS

- Primary Endpoint(s):

- Maximum tolerated dose (MTD) of rhIL-15 administered intravenously for 5 days in combination with avelumab for up to 6 cycles
- Frequency (number and percentage) of treatment-emergent AEs
- Secondary Endpoint(s):
 - Overall response rate (including CR and PR)
 - Overall response rate in patients with $\geq 50\%$ PD-L1-expressing tumor cells
 - Duration of response
 - Progression-free, event-free, and overall survival

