10.2 SAMPLE SIZE DETERMINATION

The MTD will be based on the assessment of DLT during the first cycle of treatment and will be defined as the dose level at which less than one-third of patients (0 of 3 or 0-1/6 patients) treated experience a DLT, with the next higher dose level demonstrating one-third or a greater number of patients ($\geq 2-3$ or $\geq 2-6$ patients) having a DLT. If a subject did not experience a DLT and did not finish one cycle of treatment (28 days) he or she will not be evaluable for determination of the MTD and would be replaced in the dose level. An additional 3 to 6 patients will be enrolled at the MTD, so that a total of 9 patients will be treated at this dose.

Using this dose-escalation scheme the probability of escalating to the next dose level will be based on the true rate of DLT at the current doses given by the following table (each group will be considered independently of the other); Thus, if the true underlying proportion of DLTs is 50% at the current dose there is a 17% probability of escalating to the next dose.

True toxicity at a given dose	10%	20%	30%	40%	50%	60%
Probability of escalating	0.91	0.71	0.49	0.31	0.17	0.08

If all four dose levels are evaluated with 6 patients per dose level and 9 total patients at the MTD, a maximum of 27 evaluable patients will be enrolled. Similarly, if all dose levels are evaluated with 3 patients per dose level and 9 total patients at the MTD, the minimum number of evaluable patients required will be 18. To account of unevaluable patients, accrual ceiling will be set at 30. It is expected that the accrual can be completed in 24 months.

A maximum of 30 patients will be enrolled over 24 months, at a rate of 1-2 patients per month.

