12.4 EVALUATION OF BENEFITS AND RISKS/DISCOMFORTS

The potential benefit of adding rhIL-15 to avelumab in treatment of mature T-cell malignancies is unknown, but single-agent immune checkpoint inhibitors have shown activity as outlined in Section [1.2.5](#). There is a risk of additive toxicity of the two drugs, in particular infusion reactions (including chills, fever, hypotension, headache, flushing, dizziness), fatigue, rash, Liver Function Test (LFT) abnormalities, and cytopenias.

Since fevers, rigors, lymphopenia, and LFT elevations occurred only during IL-15 infusion in the continuous IV trial, and since avelumab is not given concomitantly, these toxicities are not expected to overlap. Avelumab manufacturer recommendations for discontinuing therapy will be followed, including for grade 3-4 LFT elevations. Fatigue and rash are potential overlapping toxicities, and both will be monitored closely.

It has recently been shown that PD-1 may act as a haplo-insufficient tumor suppressor of T lymphocytes, with PD-1/PD-L1 checkpoint blockade causing transient lymphoproliferation in ITK-SYK transgenic mice(21). Clinically, three patients with ATLL treated with the anti-PD-1 antibody Nivolumab had rapid disease progression shortly after receiving the first dose (“rapid progression”). Additionally, four patients with AITL have experienced rapid progression after 1-3 doses of nivolumab.(19) Patients with ATLL, AITL, and PTCL-TFH (which has a similar phenotype to AITL) are therefore excluded from this Phase 1 trial. Additionally, growth of malignant cells in enteropathy-associated T-cell lymphoma (EATL) is dependent on epithelial cell-derived IL-15. Patients with EATL are therefore also excluded. There are ongoing trials of different immune checkpoint inhibitors in patients with other forms of T cell lymphoma with no reports of rapid progression. Study team will note any rapid and unexpected disease progression observed in patients on the trial as described in Section [6.3.4](#).

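### Does rapid progression, named a distinct outcome in section 6.3.4, need its own analysis in section 10?

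*Combined protocol and SAP*

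**What the plan says.** Section 6.3.4 states that "rapid progression will be followed as a distinct outcome". The definition follows: "Rapid progression is defined as any PD within 14 days of the first avelumab administration (i.e., up to and including Cycle 1, Day 21"), with skin flares left out. Section 12.4 adds only this: "Study team will note any rapid and unexpected disease progression observed in patients on the trial as described in Section" 6.3.4.

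Section 10.1 lists the MTD and treatment-emergent adverse events as primary endpoints. The secondary endpoints are response rate (overall and in tumors with high PD-L1), duration of response, and "Progression-free, event-free, and overall survival". Rapid progression is not among them. It has no population in section 10.3 and no summary in section 10.4, and section 10.4.8 plans no tabulation of individual participants.

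Three other rules bear on the point.

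- Section 3.8.1 gives "Confirmed disease progression" as a reason to end protocol therapy.
- Section 3.1.1 does not count toxicity that is beyond dispute due to progression as a dose-limiting toxicity (DLT).
- Section 10.2 says of a patient without a DLT who "did not finish one cycle of treatment (28 days) he or she will not be evaluable for determination of the MTD"; that patient is replaced at the same dose level.

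On numbers, section 10.2 says "a maximum of 27 evaluable patients will be enrolled" with six patients per level, and "the minimum number of evaluable patients required will be 18" with three per level. The accrual ceiling is 30.

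**The concern.** The protocol treats this event as serious. Rapid progression under PD-1 blockade is why ATLL, AITL and PTCL-TFH are excluded (section 12.4). An outcome singled out in this way would normally have a numerator, a denominator and a line in the analysis section.

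The replacement rule sharpens the worry. A patient who progresses by Day 21, stops treatment and has had no DLT drops out of the MTD tally, and another patient takes the place. A report could then state an MTD from evaluable patients and never say how many others at that dose progressed straight after avelumab. At the largest design, three replaced rapid progressors would show as 0 of 27 in the MTD set, against 3 of 30 among all patients.

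PFS and EFS include the event but run from enrollment, so the end of the window has no fixed place on those curves. The first scheduled disease evaluation also comes after Day 21, so a low count might reflect how little was looked for.

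**Working it through.** **1. The plan's own figures.** For a true DLT rate p, the 3 + 3 rule escalates with probability (1−p)³ + 3p(1−p)² × (1−p)³. For p = 10% to 60% this gives 0.906, 0.709, 0.494, 0.309, 0.172 and 0.082, which match the table in section 10.2 after rounding. The evaluable totals also reproduce: 3 × 6 + 9 = 27 and 3 × 3 + 9 = 18. The formula concerns evaluable patients only. Replacing patients who did not complete the DLT window leaves these figures as stated, provided that stopping for progression is unrelated to DLT risk.

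**2. How many patients could be replaced.** If all four levels are evaluated, the room is 30 − 27 = 3 to 30 − 18 = 12 patients, or 10% to 40% of the ceiling. This covers replacement for any reason, so it is an upper bound on replaced rapid progressors. A rapid progressor who also had a DLT stays in the MTD set. A patient with Sézary syndrome and a suspected flare continues treatment (section 6.3.3) and may stay in it too.

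**3. Where a replaced patient still appears.**

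| Output | Source | Is the patient in it? |
|---|---|---|
| MTD tally | 10.2 | No, unless a DLT occurred |
| Toxicity | 10.3.1 | Yes, all treated patients |
| Response | 10.3.2 | Yes, if progression before the end of Cycle 1 is objective |
| Response and time-to-progression reports | 10.4.3 | Yes, all patients in the study |
| PFS and EFS | 6.3.7, 6.3.9 | Yes, as an event |

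Section 6.3.3 (the CTCL criteria) starts time to progression at the start of treatment. On that axis Cycle 1 Day 21 is 21 − 1 = 20 days after Day 1 for every patient on schedule. On the PFS axis it falls 20 to 48 days after enrollment, assuming 0 to 28 days from enrollment to Day 1; the documents do not fix that gap.

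**4. What is looked for inside the window.** Avelumab is first given on Day 8, and Days 8 to 21 are 21 − 8 + 1 = 14 days. Disease evaluation is every 8 weeks, ±4 days, from the prior assessment (section 3.6, footnote 4).

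- With baseline up to 28 days before dosing (section 2.4), the first evaluation is due between Day 1 − 28 + 56 − 4 = 25 and Day 1 + 56 + 4 = 61. That is 4 to 40 days after the window closes.
- If the 14-day baseline column of the calendar governs imaging, the earliest is Day 1 − 14 + 56 − 4 = 39.

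On either reading no imaging-based evaluation is scheduled inside the window. Clinical assessment is, however. Section 3.4 requires pre-dose assessments up to 3 days before the Day 8 and Day 22 doses, so the second set can fall on Days 19 to 21. The calendar includes physical examination, blood count and LDH at those visits. For CTCL, section 6.3.3 has the same assessor score mSWAT at every study visit.

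**5. What a count could show.** Section 10.4.1 names the Agresti-Coull interval for the response rate. With ñ = n + z², p̃ = (x + z²/2)/ñ and limits p̃ ± z√(p̃(1−p̃)/ñ), z = 1.96, truncated at zero:

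- 0/30: 0 to 13.5%
- 3/30: 2.7 to 26.4%
- 0/9: 0 to 34.5%

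**The case for a change.** The best argument for a change is that section 10 does not oblige anyone to report an outcome that section 6.3.4 promises to follow, and that a denominator is better fixed before the results are known. Section 12.4 says that rapid progression has not been reported in the ongoing trials in other T-cell lymphomas, so this trial's own count would be informative. Time to progression is an imperfect stand-in: it is defined only in the CTCL section, it is not a listed endpoint, and it takes the off-treatment date for patients who stop for any reason.

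Much of this stands as description. Section 10 is silent, a labelled count is absent, and no imaging-based evaluation falls in the window.

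The inference that patients would be hidden does not stand, as step 3 shows. The denominator is not really open either. The definition is anchored on the first avelumab dose, so only patients who received avelumab can meet it, and replacement for the MTD does not remove them. The lack of individual tabulation in section 10.4.8 is weak support, because section 10.4.2 plans safety listings.

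The obvious additions would also gain little. A pooled count would not give the number at the MTD, which is the figure at issue. A companion count of progression by the first scheduled evaluation would close anywhere from Day 25 to Day 61, so it would have no fixed window. A note that nothing is scheduled before Day 21 would overlook the pre-dose examinations.

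**Conclusion.** No change to the plan follows. This is missing detail that an analyst following section 6.3.4 would supply. The event is defined, the progression and dosing dates are collected, and the count, overall or by dose level, follows from them. Section 12.4 promises only that the team will note such cases, and under section 7.4.1 the principal investigator reviews response data on every patient.

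The MTD rule is not at fault. It sets aside patients who did not complete the DLT window, and every figure in section 10.2 reproduces. No endpoint or dose decision uses rapid progression.

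The gap is limited to one descriptive count. At most 3 to 12 patients could be replaced for all reasons together, if all four levels are evaluated. Even with complete detection the upper 95% limit after no events would be 13.5% in 30 patients and 34.5% in 9. A low count should be read with caution, since detection by Day 21 rests mainly on examination. That is a matter for interpretation when the results are reported. The conclusion assumes that progression dates are recorded for replaced patients, which the PFS and EFS analyses already require.

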There is preclinical and clinical evidence to suggest that immune checkpoint inhibition may precipitate rapid progression in some forms of T-cell lymphoma, most notably those that are PD-1 (but not PD-L1) positive. In a phase II trial of nivolumab in patients with PTCL, ORR was 33%, with two CRs and two PRs among the 12 patients treated.(19) However, one of six patients with AITL progressed after the first dose, and three more experienced significant progression after the second or third dose of nivolumab. Notably, AITL tumor cells were shown to have high levels of PD-1(20), which may act as a tumor suppressor in T-cell lymphomagenesis.(21) PTCL with T follicular helper phenotype (PTCL-TFH) is another form of PTCL in which tumor cells are PD-1 positive, as is ATLL. A trial of single-agent nivolumab for ATLL (NCT02631746) was suspended for interim analysis when the first 3 patients enrolled developed accelerated disease progression within the first two doses of the drug.(22)

There are several ongoing Phase 2 trials that have yet to report results: nivolumab for relapsed/refractory PTCL (NCT03075553), pembrolizumab after auto-SCT for any HL, DLBCL, and T-NHL (NCT02362997); pembrolizumab for CTCL in combination with romidepsin (NCT03278782), radiation therapy (NCT03385226), and decitabine and pralatrexate (NCT03240211, which also includes patients with PTCL); atezolizumab for relapsed/refractory CTCL (NCT03357224); and avelumab for relapsed/refractory PTCL (NCT03046953).

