2.4 BASELINE EVALUATION

The following should be performed within 28 days prior to the first dose of rhIL-15 unless otherwise noted; tests performed as part of screening do not need to be repeated if they were performed within the specified window prior to initiating treatment.

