3 STUDY IMPLEMENTATION

3.1 STUDY DESIGN

In patients with relapsed or refractory T-cell malignancies, IL-15 will be administered by continuous intravenous infusion in a dose-escalation 3 + 3 system with a starting dose of 1 mcg/kg/day, a second dose level of 2 mcg/kg/day, a third dose level at 3 mcg/kg/day, and a fourth dose level at 4 mcg/kg/day on days 1-5 of each of six cycles. Avelumab (IV over 1 hour) will be administered at a dose of 10 mg/kg on days 8 and 22 of the cycle. Treatment will continue for a maximum of 6 cycles or until toxicity (i.e., dose limiting toxicity as found in Section 3.1.1 or toxicity requiring hold as defined in Section 3.3) or progressive disease.

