NOTE: Any other tests should be performed as clinically indicated. See Section 3.2 for drug administration information. See Section 5 for information on research blood samples/correlative studies to be collected.

¹ 30 days (± 7) following last dose, and 90 days ($+14$) after last dose of avelumab (via clinic or phone). If initiating new anti-cancer therapy within 30 days after last dose of avelumab, 30-day safety follow-up visit must occur before first dose of new therapy.

² Screening and Baseline evaluations should be performed within 28 days prior to enrollment and dosing, respectively, unless otherwise noted and with the following exceptions: Confirmation of diagnosis (no time limit); HIV antibody, HTLV-1/2 serologies, Hepatitis B surface antigen and Hepatitis C antibody, EKG, and bone marrow aspiration/biopsy (all within 3 months) **NOTE:** Any screening tests performed within the specified time frame for baseline do not need to be repeated.

³ Within 14 days prior to dosing on C1D1, with the following exceptions: Pregnancy test (within 7 days of dosing; must be negative).

⁴ ± 4 days, from date of prior assessment. Confirmatory scans should also be obtained 4 weeks following initial documentation of objective response. After completion of treatment, imaging assessment will be performed at each scheduled post-treatment follow-up visit for up to 3 years.

⁵ To be done at end of treatment (30 days after last dose of study treatment; may be combined with 30 day safety follow-up, if timing coincides). If subject to initiate new anti-cancer therapy assessments should occur before the first dose of the new therapy.

⁶ Follow-up to occur about every 60 days (± 7 days) for first 6 months, every 90 days (± 14 days) for 2 years, then every 6 months (± 28 days) for another 2 years and then annually (± 6 weeks) until disease progression or initiation of new anti-cancer therapy. After completion of treatment, imaging assessment will be performed at each scheduled post-treatment follow-up visit for up to 3 years.

⁷ After disease progression or initiation of new anti-cancer therapy, contact for survival about every 3 to 6 months (± 4 weeks).

⁸ Pathologic review/confirmation of diagnosis by Laboratory of Pathology, NCI (no time limit). If archival sample is not available, a fresh tumor biopsy and/or peripheral blood sample will be obtained.

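### The rapid-progression window in Section 6.3.4 ends before avelumab dose 2 and before any scheduled disease evaluation, so the outcome is likely under-ascertained and does not match how Section 12.4 uses the term.

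*Combined protocol and SAP*

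**What the plan says.** Section 6.3.4 tracks rapid progression as an outcome in its own right: "Rapid progression is defined as any PD within 14 days of the first avelumab administration", with Cycle 1 Day 21 given as the last day. Skin flares are excluded, but a suspected flare that is later confirmed as progression is counted. The clinical reason given there is three ATLL patients treated with nivolumab, described as progressing soon after dose 1.

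Section 3.1 says that avelumab "will be administered at a dose of 10 mg/kg on days 8 and 22 of the cycle". The Study Calendar (Section 3.6) sets disease evaluations every 8 weeks, with a tolerance of plus or minus "4 days, from date of prior assessment". It lists no imaging, skin scoring or flow cytometry for disease in Cycle 1. For baseline procedures, Section 2.4 says: "The following should be performed within 28 days prior to the first dose of rhIL-15 unless otherwise noted".

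Two other sections describe the cases behind the worry. Section 1.2.5 says that one of six AITL patients progressed after the first nivolumab dose and that "three more experienced significant progression after the second or third dose of nivolumab". It places the three ATLL cases within the first two doses. Section 12.4 says that "four patients with AITL have experienced rapid progression after 1-3 doses of nivolumab", repeats the after-dose-1 description of the ATLL cases, and refers to Section 6.3.4 for how such progression will be noted.

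Rapid progression is not among the endpoints in Section 10.1 or the analyses in Section 10.4, so no denominator is stated.

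**The concern.** The outcome exists because checkpoint blockade may speed up some T-cell lymphomas. To inform that question, its window should cover the kind of event that the protocol itself calls rapid progression, and there should be a planned opportunity to see it. The definition is narrower than the usage in Section 12.4, which counts events after doses 2 and 3. It also closes before the first planned look at the disease.

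What is at stake is the meaning of a low count. Section 12.4 supports enrolling the remaining histologies partly on the absence of such reports from other trials. A count of zero or one here could be read as further reassurance when it partly reflects a short window and no scheduled assessment within it.

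**Working it through.** **1. The plan's own figure.** First avelumab is on Day 8. Counting the dose day as day 1 of 14, the last day is 8 + 14 − 1 = Day 21, which reproduces Section 6.3.4. Counting elapsed days gives 8 + 14 = Day 22, the day of dose 2. The plan does not state the counting rule, and the fixed Day 21 fits only if the first dose is given exactly on Day 8.

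**2. Dose days (Section 3.1, 28-day cycles, no delay).** Dose 2 is Day 22, one day after the window closes. Dose 3 is 28 + 8 = Day 36.

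**3. First scheduled disease evaluation.** If baseline imaging is done b days before Cycle 1 Day 1, with b from 0 to 28, and there is no Day 0:

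study day = 1 − b + 56 ± 4

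| Baseline, days before C1D1 | Earliest | Nominal | Latest |
|---|---|---|---|
| 28 | 25 | 29 | 33 |
| 14 | 39 | 43 | 47 |
| 0 | 53 | 57 | 61 |

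The range is Day 25 to Day 61, or 17 to 53 days after first avelumab. No permitted baseline date puts a scheduled evaluation inside Days 8 to 21.

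**4. Cited cases, by the dose they followed.**

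| Cases | After a dose later than dose 1 |
|---|---|
| AITL (Section 1.2.5) | 3 of 4 (75%) |
| ATLL, wording of Sections 6.3.4 and 12.4 | 0 of 3 |
| ATLL, wording of Section 1.2.5 | 0 to 3 of 3 |
| All seven, wording of Sections 6.3.4 and 12.4 | 3 of 7 (43%) |
| All seven, wording of Section 1.2.5 | 3 to 6 of 7 (43% to 86%) |

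**5. How much ordinary progression a wider count would include.** From Day 8 to Day 61 is 53 days. As an illustration only, assume a constant hazard and the median PFS values that Section 1.2.2 reports for approved PTCL agents: 1.6 months (1.6 × 30.4 = 48.6 days) and 4 months (4 × 30.4 = 121.6 days). The share progressing is 1 − 2^(−53/48.6) = 53% at the short median and 1 − 2^(−53/121.6) = 26% at the long one.

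**The case against.** The strongest defence is that no scheduled scan does not mean no detection. The Day 22 pre-dose assessments may be done up to 3 days early (Section 3.4), so an examination can fall on Days 19 to 21. The calendar allows further tests when the clinical picture calls for them. The team discusses each patient at least weekly (Section 7.4.1). Section 10.3.2 expressly provides for objective progression before the end of Cycle 1. A flare suspected inside the window can be confirmed 2 to 4 weeks later (Section 6.3.3) and still count. All of this stands. A reader might infer that a null result is close to guaranteed by the design; these provisions show that it is not.

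The limit of the defence is that detection inside the window rests on unscheduled work-up or a visit brought forward. Under RECIL 2017 (Section 6.3.2), progression needs a measured increase of more than 20% in summed diameters or a new lesion, which will often require imaging.

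A second objection is that Section 6.3.4 cites only the ATLL cases and describes them as following dose 1, so on its own terms the window is not inconsistent with them. That also stands for Section 6.3.4 read alone. It does not settle the mismatch with Section 12.4, which applies the same term to the AITL cases and refers to the same definition.

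Third, later progression is not lost: it enters PFS and EFS, and rapid progression drives no decision rule. This is correct and limits the consequence to interpretation. It does not supply the separate early count that the protocol set out to make.

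**Conclusion.** The window closes one day before scheduled dose 2 and at least 4 days before the earliest scheduled disease evaluation (Day 25 against Day 21). It excludes progression after dose 2 or 3, which describes 3 of the 4 AITL cases that Section 12.4 calls rapid progression. The outcome is likely under-ascertained, and a low count would be hard to interpret.

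A reader might infer that the window would miss most of the cited cases. The documents do not establish that. The share clearly following a later dose is 3 of 7; it exceeds half only if at least one ATLL case followed dose 2, which Section 1.2.5 permits but does not state. The documents give neither days to progression nor the nivolumab interval, so no cited case can be placed on this trial's calendar. ATLL and AITL are also excluded here, so these shares describe the fit of the definition to its rationale. They do not predict a miss rate among enrolled patients.

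The day counts assume avelumab on schedule from Day 8, no Day 0, and baseline assessment within the 28 days allowed.

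**What to change.** In Section 6.3.4:

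- Keep the 14-day count and state its counting rule.
- Add a nested descriptive count of progression or lymphoma death from first avelumab through one cut-off common to all patients. The cut-off should take in dose 3 (Day 36) and the latest permitted first evaluation; about Day 61, 53 days after first avelumab, does both. Ending at each patient's own first evaluation would give unequal windows, from about Day 25 to Day 61, some closing before dose 3.
- Report both counts with denominators by histology, using the diagnostic groups of Section 10.4.7.
- List the date of each patient's first post-baseline evaluation, and whether progression was found at a scheduled or unscheduled assessment.

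Reconcile Sections 1.2.5, 6.3.4 and 12.4 on the timing of the ATLL cases.

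The cost is protocol wording, an added table line and a short listing. No scans are added and treatment is unchanged. The downside is that the wider count includes a material share of ordinary early progression, roughly a quarter to a half under the illustration above. It cannot by itself separate acceleration from natural history, so it should be labelled descriptive and shown beside the 14-day count.
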